7.1.1 Statistical Rationale

The purpose of the clinical trial per se is to reject the combination of lenalidomide and nivolumab from further clinical development if the therapy is insufficiently active. The trial is designed as a Sargent one-stage, three-outcome design⁴³ with the following assumptions: the inactivity cut off of the combination is 26% (the previously published, single-agent, objective response rate of lenalidomide in relapsed MM) and the activity cut off is 60% (the previously published, objective response rate of lenalidomide in combination with dexamethasone in the setting of relapsed MM). The type 1 (alpha) and type 2 (beta) error rates are both set to 5%, the probability of correctly rejecting an ineffective treatment is set to 80%. Under these assumptions, the three-outcome design specifies treatment of n=18 pts in this phase II trial. If n=7 or fewer show response to treatment, the combination will be declared ineffective. If n=10 or more pts show objective response, the treatment will be declared effective. If n=8 or 9 pts show response, the trial will be deemed inconclusive and additional pts may be enrolled.

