The proportion of responses (partial and complete) will be calculated out of all eligible patients who receive any treatment in that disease group who are included in the phase II assessment. Assuming the number of responses is binomially distributed, 95% binomial confidence intervals will also be calculated for the estimate of the proportion of responses. All adverse events will be summarized by the NCI CTCAE v. 4 criteria, and tabulated across all patients who received any treatment with a focus on severe (grade 3+) adverse events and toxicities (i.e. those deemed at least possibly related to study treatment). In addition, we will summarize the proportion of patients who received dexamethasone after being stable disease but without response after 2 cycles of therapy. We will descriptively summarize how many of these patients were converted to response after the addition of dexamethasone. Since the addition of dexamethasone is part of the overall treatment regimen that is dependent on treatment outcome at a certain time point, we will not make other adjustments to the study design to evaluate these patients separately outside of this descriptive summarization of whether or not they received the dexamethasone. We will evaluate other clinical outcomes such as progression-free survival and overall survival using the methods of Kaplan-Meier, although these analyses will be exploratory and primarily to help describe the cohort itself.

Correlative analyses will also be done, including analysis of markers of the immunogenicity of nivolumab. In particular, we will evaluate biological and cellular markers in patients treated with nivolumab, measure PD-L1 expression on MM cells, percentage increase in NK cell activity, migration, immune complex formation, and cytotoxicity. Other markers such as plasma cell IHC baseline expression to characterize immunologic markers of MM cells that are responsive to nivolumab such as TNF-alpha, IFN-gamma, CD4, CD8, and granzyme B will be evaluated in addition to markers of MM cells responsive to lenalidomide (Sparc, IRF-4). Changes in these markers before and after therapy will be explored using graphical analyses as well as summarized quantitatively. We will also explore how changes in these correlative markers may differ based on whether or not the patient achieved a response or not; to accomplish this, we will utilize different plotting characters and colors for successes

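### The 18-patient decision rule does not follow from its stated inputs: both cut-offs sit one response too high, which costs about 13 points of power at the top and puts beta at 5.76% at the bottom

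*Combined protocol and SAP*

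**What the plan says.** Section 7.1.1 (Statistical Rationale) states: "The trial is designed as a Sargent one-stage, three-outcome design". The inactivity rate is 26%, taken from published single-agent lenalidomide. The activity rate is 60%, taken from published lenalidomide plus dexamethasone. On error rates: "The type 1 (alpha) and type 2 (beta) error rates are both set to 5%, the probability of correctly rejecting an ineffective treatment is set" at 80%. The section says that these assumptions yield 18 patients and a three-way rule. Seven or fewer responses means ineffective. For the top category, "If n=10 or more pts show objective response, the treatment will be declared effective". Between them, "If n=8 or 9 pts show response, the trial will be deemed inconclusive and additional pts may be enrolled".

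The section prints no attained error rate for either cut-off, no target for the probability of declaring a 60% regimen effective, and no decision rule for the added patients. It also plans interval estimation: "Assuming the number of responses is binomially distributed, 95% binomial confidence intervals will also be calculated for the estimate of the proportion of responses".

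**The concern.** A cut-off presented as the product of a 5% alpha should be the one that a 5% alpha gives, or the plan should say why it is stricter. Ten of 18 is 56%, a long way above a 26% null, which suggests that much of the alpha is unspent. In a three-outcome design beta is the chance of declaring an active regimen ineffective. A printed beta of 5% therefore does not tell the reader how often an active regimen is declared effective. That probability has to be computed from the rule.

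This is the trial's only formal efficacy decision. If the upper bar is higher than the inputs need, an active combination is more likely to end as inconclusive, with an extension that has no specification. If the lower bar is too high, an active combination is dropped slightly more often than the plan says.

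**Working it through.** **Inputs, all from 7.1.1:** n = 18; p0 = 0.26; p1 = 0.60; alpha ≤ 0.05; beta ≤ 0.05; P(ineffective | p0) ≥ 0.80; binomial counts. Sidedness is not stated. The efficacy rule is an upper-tail rule, so it is treated as one-sided.

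**Formula:** P(X ≥ k | p) = Σ from j = k to 18 of C(18, j) p^j (1 − p)^(18 − j). Then alpha = P(X ≥ upper | 0.26), beta = P(X ≤ lower | 0.60), and correct rejection = P(X ≤ lower | 0.26).

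**Step 1: the printed rule (≤7 / 8–9 / ≥10).**
- alpha = P(X ≥ 10 | 0.26) = 0.0073
- P(effective | 0.60) = P(X ≥ 10 | 0.60) = 0.7368
- P(inconclusive | 0.60) = P(8) + P(9) = 0.0771 + 0.1284 = 0.2055
- beta = P(X ≤ 7 | 0.60) = 0.0576, above 0.05
- correct rejection = P(X ≤ 7 | 0.26) = 0.9301

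**Step 2: the upper cut-off.**

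| Effective if | alpha at 26% | P(effective) at 60% |
|---|---|---|
| ≥8 | 6.99% | 94.2% |
| ≥9 | 2.49% | 86.5% |
| ≥10 (printed) | 0.73% | 73.7% |

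Nine is the smallest count within 5%. The step from 10 to 9 is worth 86.5 − 73.7 = 12.8 points at 60%. At a true rate of 50% it moves P(effective) from 40.7% to 59.3%. An exact two-sided 5% also gives 9. Normal approximations, with and without continuity correction, give 8 or 9. None of these gives 10.

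**Step 3: the lower cut-off.**

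| Ineffective if | beta at 60% | correct rejection at 26% |
|---|---|---|
| ≤5 | 0.58% | 68.2% (below 80%) |
| ≤6 | 2.03% | 83.7% |
| ≤7 (printed) | 5.76% (above 5%) | 93.0% |

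Six is the only lower cut-off at n = 18 that meets both limits.

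**Step 4: the pair ≤6 / 7–8 / ≥9.** Alpha 2.49%, beta 2.03%, correct rejection 83.7%, P(effective | 60%) 86.5%, P(inconclusive | 60%) 11.4%. Every printed constraint is met. Moving only the upper cut-off to 9 would leave beta at 5.76%.

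**The case against.** The strongest reply is that the upper cut-off breaks nothing. An attained alpha of 0.73% satisfies a 5% limit, and no power target is printed for 73.7% to miss. The stated purpose is to screen out an inactive combination, and a demanding bar for *effective* is compatible with that. All of this stands. A reader might infer that the trial violates its type I error or fails a promised power; the documents support neither. What remains is that the section presents 10 as the consequence of inputs that give 9, and offers no reason for the extra strictness.

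A reader might also see a contradiction with the planned interval, since 9 of 18 has an exact 95% interval of 26.02% to 73.98%, which excludes 26%, while the rule calls the result inconclusive. This is weak. The margin is 0.02 points against a rounded published rate, and the plan uses the interval for estimation, not for the decision.

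Two further objections stand as limits. First, results of 8 or 9 are not failures, because more patients may be enrolled. So 2.49%, 73.7% and 86.5% describe the first 18 patients, not the whole trial. If every inconclusive result were later turned into *effective*, the type I error could reach P(X ≥ 8 | 26%) = 6.99% under the printed rule and P(X ≥ 7 | 26%) = 16.3% under the re-derived one.

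Second, 26% is a single-agent lenalidomide rate, but dexamethasone may be added after two cycles, before the cycle-4 assessment. The documents give no null rate for this regimen and population. Taking 30% and 35% as assumptions, alpha at ≥9 would be 6.0% and 13.9%, against 2.1% and 6.0% at ≥10. The requirement of at least four prior lines could push the null the other way. Strictness may therefore be defensible, but then it should be stated and justified.

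**Conclusion.** The concern holds as a mismatch between the stated inputs and the stated rule, with both cut-offs one response too high. At the upper boundary the consequence is lost power, 12.8 points at the design alternative, with no limit exceeded. At the lower boundary a printed limit is exceeded, by a small amount: 5.76% against 5%.

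The result assumes 18 evaluable patients, the response definition in 7.1.1 (partial and complete responses; section 7.3 also counts stable disease), the usual three-outcome meaning of alpha and beta, and a null of exactly 26%. It does not show that the trial is invalid or that 18 patients are too few, since 18 suffice for every printed constraint. The matter should be corrected before the decision rule is applied.

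**What to change.** In 7.1.1, re-derive the two cut-offs together. One rule that meets every printed constraint at n = 18 is: ineffective at 6 or fewer responses, inconclusive at 7 or 8, effective at 9 or more. Print the attained values with it: alpha 2.5%, beta 2.0%, correct rejection at 26% of 83.7%, P(effective | 60%) 86.5%.

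If the sponsor keeps the printed rule, leave the design limits in place and add the attained values beside them: alpha 0.7%, beta 5.8%, P(effective | 60%) 74%, inconclusive at 60% 21%, with the reason for the stricter upper bar.

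In either case, state that these figures apply to the first 18 patients, and either give a size and decision rule for any extension or say that none exists.

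Cost: a few sentences and no extra patients. The re-derived rule raises attained alpha from 0.7% to 2.5%, within the stated 5% at a 26% null but with less margin if the true null is higher. It also lowers correct rejection at 26% from 93.0% to 83.7% and raises the inconclusive share there from 6.3% to 13.8%, so the missing extension rule matters more.

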7.2 Safety Endpoints

We will describe the safety profile of treatment by the recording of adverse events experienced by patients in the trial and by the monitoring of clinical laboratory values. The safety analysis will be performed on the safety population, as defined below. Adverse events will be described using the NCI CTCAE V 4.0 criteria.

Laboratory assessments will also be described according to the NCI CTCAE criteria, with separate descriptions for grade 3 or 4 laboratory abnormalities. Clinically significant laboratory abnormalities will be described as well.

7.3 Clinical outcome definitions

Time to progression: TTP will be defined as the time from start of treatment until the date he or she has progression or dies. Any subject who has received study treatment but has neither progressed nor died will be censored on the date of his or her last tumor assessment. A subject who has not received study treatment and who has neither progressed nor died will be censored on the day he or she was enrolled.

Progression Free Survival: PFS will be defined as the time from study entry until disease progression or death at trial closure for the per protocol population. Patients who withdraw from the trial prior to disease progression and who are either lost to follow-up, die or who begin alternative treatments prior to progression, will have their data censored as of the date considered to be lost to follow-up, date of death, or the first day of alternative therapy.

Time to Response: A subject's time to response is defined as the time from first dose of study therapy until measurement criteria are first met for [VG]PR or CR or SD (whichever status is recorded first). Time to response is computed only for subjects whose best response is [VG] PR or CR.

Duration of Overall Response: The duration of overall response will be computed for subjects whose best response is either [VG] PR or CR or SD. It will be measured from the time measurement criteria are first met for complete response or partial response (whichever status is recorded first) until the first date of progressive disease or death. Subjects who neither progress nor die will be censored on the date of their last tumor assessment.

Overall Survival: A subject's survival time will be defined as the time from start of treatment to the date of his or her death. If the subject has not died, survival will be censored on last date the subject was known to be alive.

Response Rate: The tumor response rate will be defined as the total number of subjects whose best response is PR or VGPR or CR or SD, divided by the number of per protocol patients.

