Relapse from CR ⁱ	Any one or more of the following: 
 • Reappearance of serum or urine M-protein by immunofixation or electrophoresis • Development of $\ge 5\%$ plasma cells in the bone marrow^j • Appearance of any other sign or progression

a. All response categories require two consecutive assessments made at anytime before the institution of any new therapy; all categories also require no known evidence of progressive or new bone lesions if radiographic studies were performed. Radiographic studies are not required to satisfy these response criteria.

b. Confirmation with repeat biopsy not necessary.

c. Presence/absence of clonal cells is based upon the κ/λ ratio by immunohistochemistry and/or immunofluorescence requires a minimum of 100 plasma cells for analysis. An abnormal ration reflecting presence of an abnormal clone is κ/λ of $> 4:1$ or $< 1:2$.

d. Applicable only to patients who have 'measurable' disease defined by at least one of the following three measurements: Serum M-protein $\ge 1 \text{ g/dl}$, Urine M-protein $\ge 200 \text{ mg/24hour}$, Serum FLC assay involved FLC level $\ge 10 \text{ mg/dl}$ provided serum FLC ration is abnormal.

e. Not recommended for use as an indicator of response; stability of disease is best described by providing the time to progression estimates).

f. All relapse categories require two consecutive assessments made at anytime before classification as relapse or disease progression and/or the institution of any new therapy.

g. For progressive disease, serum M-component increases of $\ge 1 \text{ gm/dl}$ are sufficient to define relapse if starting M-component is $\ge 5 \text{ g/dl}$.

h. Relapse from CR has the 5% cutoff versus 10% for other categories or relapse.

i. To only be used if the end point studied is disease free survival. For purposes of calculating time to progression and progression-free survival, CR patients should also be evaluated using criteria listed above for progressive disease.

j. Relapse from CR has the 5% cutoff versus 10% for other categories of relapse.

14 Appendix. NYHA Cardiac Disease

Class	Functional Capacity	Objective Assessment
I	Patients with cardiac disease but without resulting limitations of physical activity. Ordinary physical activity does not cause undue fatigue, palpitation, dyspnea, or anginal pain.	No objective evidence of cardiovascular disease.

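### Section 7.3 counts stable disease as response, censors some deaths in PFS and counts deaths in TTP, out of line with the rest of the protocol

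*Combined protocol and SAP*

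**What the plan says.** All five definitions stand in section 7.3 of the combined protocol and SAP.

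- **Response Rate** is "the total number of subjects whose best response is PR or VGPR or CR or SD, divided by the number of per protocol patients". No per protocol population is defined. Section 7.1.1 counts only partial and complete responses, over every eligible patient given any treatment. Appendix 13, note e, says of SD: "Not recommended for use as an indicator of response".
- **Time to response** runs from first dose until the criteria are first met for [VG]PR "or CR or SD (whichever status is recorded first"). It is computed only for patients whose best response is [VG]PR or CR.
- **Duration of response**: "The duration of overall response will be computed for subjects whose best response is either" [VG]PR, CR or SD. The clock starts at the first CR or PR.
- **PFS**: "PFS will be defined as the time from study entry until disease progression or death at trial closure for the per protocol population". The next sentence covers patients who withdraw before progression. Those "who are either lost to follow-up, die or who begin alternative treatments prior to progression, will have their data censored", and for those who die the censoring date is the date of death.
- **TTP**: "TTP will be defined as the time from start of treatment until the date he or she has progression or dies".

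Section 2.4 lists TTP and PFS as secondary endpoints. It does not list time to response or duration of response. Section 7.1.1 calls the PFS and OS analyses exploratory.

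**The concern.** An analyst programming from 7.3 would produce a second response rate that differs from 7.1.1 in both numerator and denominator. Time to response could be dated before the response. Duration of response could not be computed for some of the patients it includes. PFS would drop some deaths that TTP keeps, the reverse of what the two names imply. Response rate is the primary endpoint, so the first item matters most: if the 7.3 rate were carried into the decision rule, SD would count towards declaring the combination effective.

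**Working it through.** **1. The plan's own rule (section 7.1.1).** Inputs: n = 18, cut-offs 26% and 60%, ineffective at 7 or fewer responses, effective at 10 or more. With X binomial:

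- P(X ≥ 10 | 0.26) = 0.0073 and P(X ≤ 7 | 0.26) = 0.9301
- P(X ≤ 7 | 0.60) = 0.0576 and P(X ≥ 10 | 0.60) = 0.7368

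The first figure is well under the stated 5% type 1 error. The second exceeds the stated 80%. The third is slightly over the stated 5% type 2 error. The point made here does not depend on that.

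**2. What counting SD would do to the rule.** Keep the true rate of PR or better at 26% and add an assumed SD share s, so p = 0.26 + s. The documents give no SD rate for this regimen.

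| Assumed SD | p | P(X ≥ 10 of 18) |
|---|---|---|
| 0% | 0.26 | 0.0073 |
| 10% | 0.36 | 0.071 |
| 20% | 0.46 | 0.281 |
| 30% | 0.56 | 0.611 |
| 40% | 0.66 | 0.880 |
| 50% | 0.76 | 0.985 |

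Section 1.4.2 shows the contrast in reported data. For nivolumab alone it gives 17 (63%) SD and 1 (4%) CR, which fits the 27 myeloma patients. The 7.3 definition gives (17 + 1)/27 = 67%; the 7.1.1 definition gives 1/27 = 4%.

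**3. Time to response.** Section 5.1 assesses response at the end of each 28-day cycle. The study calendar (section 6.9.6, note m) starts dexamethasone in cycle 3 only after SD at two cycles, and section 7.1.1 will count how many of these patients convert to response. Moving from SD to response is therefore a planned path. Appendix 13, note a, adds: "All response categories require two consecutive assessments made at anytime before the institution of any new therapy". Take SD at cycles 1 and 2 and a first PR at cycle 3 or 4:

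- Dated at the first assessment: day 28 instead of 84 or 112. 1 − 28/84 = 67%; 1 − 28/112 = 75% too short.
- Dated at the confirming assessment: day 56 instead of 112 or 140. 1 − 56/112 = 50%; 1 − 56/140 = 60% too short.

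With SD at cycle 1 only and PR at cycle 2, the error is 50% (1 − 28/56) on the first reading and nil on the second, because that SD is never confirmed.

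**4. Duration of response.** A patient whose best response is SD never reaches CR or PR, so the clock has no start. Patients with PR or better are unaffected.

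**5. PFS.** The rule touches only patients who leave without progression, start no new therapy, stay in follow-up and then die. Let D be all PFS events, including k such deaths. Under constant hazards the median is ln 2 × (time at risk)/(events). Censoring the k deaths leaves time at risk unchanged, so the median is multiplied by D/(D − k). D and k are assumptions:

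| | k = 0 | k = 1 | k = 2 |
|---|---|---|---|
| D = 18 | 1.000 | 18/17 = 1.059 | 18/16 = 1.125 |
| D = 12 | 1.000 | 12/11 = 1.091 | 12/10 = 1.200 |

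The Kaplan-Meier median need not move at all: it stays the same if the k deaths fall after it. For scale, with 18 events and an assumed true median of 5 months, the 5th to 95th percentile range of the estimated median is about 2.5 to 7.8 months. The range scales with the median. At the 3.9 and 7.7 months in section 1.3.1 it is about 1.9 to 6.1 (× 3.9/5) and 3.8 to 12.0 (× 7.7/5).

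**6. TTP beside PFS.** TTP treats every death without progression as an event. PFS does so except after withdrawal. As written, TTP can only count as many deaths as PFS or more, and it does not measure progression alone.

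**The case against.** The strongest reply is that the primary analysis is not in doubt. Sections 2.1 and 2.3 tie the primary endpoint to IMWG criteria. Section 5.2 separates patients who responded, completely or partially, from those with stable disease. Section 7.1.1 requires objective responses for the effective boundary and describes stable patients as being without response. This stands: no clause gives precedence, but the text points consistently to PR or better. The figures in step 2 are therefore counterfactual, and 63% SD on nivolumab alone is not a forecast for the combination.

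The PFS sentence can also be read as a general rule with an exception for withdrawn patients, which is not a strict contradiction. That is a fair reading, but the exception still censors patients at the very event the endpoint counts. The size is fragile too: k may be 0, D is unknown, and follow-up after withdrawal is only where possible (section 6.8), although section 6.9.3 provides for clinic visits or phone interviews.

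A reader might infer that TTP and PFS are one endpoint under two names. The documents do not support that: they differ in time origin, deaths counted, censoring at new therapy and stated population.

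Finally, PFS is exploratory, and time to response and duration are not listed endpoints. This lowers the weight of those items. It does not make the definitions usable.

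**Conclusion.** The definitions in 7.3 should be corrected. The Response Rate item carries the most weight because it conflicts with the primary analysis in both numerator and denominator. The time-to-response and duration faults follow directly from the wording. For patients with SD at cycles 1 and 2 and a first PR at cycle 3 or 4, time to response is 50% to 75% too short, depending on whether the first or the confirming assessment sets the date. The PFS rule can only lengthen PFS, by D/(D − k) under constant hazards; the documents fix neither number, and at this sample size one or two such deaths would be small beside the imprecision of the median.

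Two stronger conclusions are tempting and not supported. One is that the trial's decision rule is compromised: it is not, provided 7.1.1 is followed. The other is that PFS ignores deaths in general: deaths without prior withdrawal remain events.

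**What to change.** Reword section 7.3 only:

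- **Response Rate, time to response, duration of response:** remove SD from all three. Define Response Rate as PR or better over all eligible treated patients, as in 7.1.1. State whether the response date is the first or the confirming assessment.
- **PFS:** count any death without prior progression or new therapy as an event, whether or not the patient had withdrawn. Keep the existing censoring at loss to follow-up and at new therapy.
- **TTP:** make progression the only event. Censor deaths without progression at the last disease assessment, the date 7.3 already uses for treated patients with no event.
- **Both TTP and PFS:** use start of treatment as the single start date, as TTP and OS already do, and all eligible treated patients as the single population, replacing the undefined per protocol set.

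The cost is a protocol amendment with IRB approval (section 16.2), with no new data, visits or patients. Reported PFS may be shorter, time to response longer, and any response rate reported under 7.3 lower.

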1.3.1 Clinical Experience in Relapsed Multiple Myeloma

A multicenter, open-label, randomized phase 2 study evaluated 2 doses of lenalidomide for relapsed, refractory multiple myeloma patients. Seventy patients were randomized to receive oral lenalidomide either 30 mg once-daily or 15 mg twice-daily for 21 days of every 28-day cycle. Patients with progressive or stable disease after 2 cycles received dexamethasone. Analysis showed an increased grade 3/4 myelosuppression in patients receiving 15 mg twice daily as compared to those receiving

30mg daily (41% versus 13%, $P = .03$). Responses were evaluated according to European Group for Blood and Marrow Transplantation (EBMT) criteria. Overall response rate (complete, partial, or minor) to lenalidomide alone was 25% (24% for once daily and 29% for twice-daily lenalidomide). Median overall survival (OS) in the 30-mg once-daily and twice-daily groups was 28 and 27 months, respectively. Median progression free survival was 7.7 months on once-daily versus 3.9 months on twice-daily lenalidomide ($P = 0.2$). Dexamethasone was added in 68 patients and 29% responded. Time to first occurrence of clinically significant grade 3 / 4 myelosuppression was shorter in the twice daily group (1.8 vs 5.5 months, $P = .05$). Significant peripheral neuropathy and deep vein thrombosis each occurred in only 3%. Lenalidomide was active and well tolerated in relapsed, refractory myeloma, with the 30-mg once-daily regimen providing the basis for future studies as monotherapy and with dexamethasone¹⁸.

In a safety and efficacy study of single agent lenalidomide in relapsed and refractory multiple myeloma patients, lenalidomide 30 mg (days 1-21 of 28 day cycle) was given to 222 patients who had relapsed or progressed after 1 or more prior therapies¹⁹. Sixty-seven percent of patients had had three or more prior therapies, and 45% had had one or more autologous stem cell transplants. Eighty and 43% of patients had had thalidomide and bortezomib based therapies respectively. The median dose of lenalidomide was 25 mg (5-30mg) and the median duration of treatment was 4.2 months (0.06-38). The overall response rate (complete and partial) was 26% with 2% complete response¹⁹.

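### Section 7.3 counts stable disease as response over an undefined per-protocol population, while 7.1.1 counts partial and complete responses over eligible treated patients

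*Combined protocol and SAP*

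**What the plan says.** Section 7.3 (Clinical outcome definitions) gives the response rate this way: "The tumor response rate will be defined as the total number of subjects whose best response is PR or VGPR or CR or SD". It sets no time limit on best response. That count is then "divided by the number of per protocol patients", and no part of the document defines the per-protocol population.

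Section 7.1.1 (Statistical Rationale) gives a different proportion: "The proportion of responses (partial and complete) will be calculated out of all eligible patients who receive any treatment", followed by a further restriction, "in that disease group who are included in the phase II assessment". It attaches 95% binomial intervals to this proportion. The decision rule in the same section covers 18 patients: 7 or fewer responses means ineffective, 8 or 9 inconclusive, and "If n=10 or more pts show objective response, the treatment will be declared effective".

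The inactivity cut-off of 26% is traced to a single-agent lenalidomide study described in section 1.3.1: "The overall response rate (complete and partial) was 26% with 2% complete response". The activity cut-off is 60%. Section 2.1 places the primary endpoint after 4 cycles, by IMWG criteria.

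**The concern.** The trial has one arm, and its conclusion rests on one proportion. The plan defines that proportion in two ways that differ in three respects.

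- **Numerator.** Section 7.3 includes stable disease (SD) and 7.1.1 does not.
- **Denominator.** Section 7.3 uses an undefined per-protocol set. Section 7.1.1 uses eligible treated patients, with a trailing restriction to a disease group and a phase II assessment. That restriction has no stated meaning in a single-disease phase II trial.
- **Timing.** Section 7.3 uses best response at any time. Section 2.1 fixes 4 cycles. Section 7.1.1 gives no time point.

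A rate that includes SD is a disease-control rate. Set beside cut-offs derived from objective response, it will tend to make an inactive combination look active. A reader who wants to know what counts as a response would naturally turn to the section headed as outcome definitions, which is where the SD wording stands.

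The same wording damages two other definitions in 7.3. Time to Response can stop at the first record of SD in a patient who responds later. Duration of Overall Response admits patients whose best response is SD, but its clock starts at first complete or partial response, so those patients have no start date.

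**Working it through.** **1. How the rest of the plan treats SD**

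| Place | Treatment of SD |
|---|---|
| 7.3, Response Rate | Counted as response |
| 7.1.1, dexamethasone summary | Described as being without response; later conversion to response is to be counted |
| Synopsis and 5.2, end of cycle 4 | Listed separately from complete or partial response |
| Appendix 13, SD row | Defined by failing CR, VGPR, PR and progression |
| Appendix 13, footnote e | Not recommended as an indicator of response |
| 1.3.1, source of the 26% | Complete plus partial only |

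Section 7.3 stands alone. Under it, the stable patients whom 7.1.1 watches for conversion after dexamethasone would already be responders.

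**2. The decision rule as written in 7.1.1**

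Inputs: n = 18, cut-offs 7 and 10, p0 = 0.26, p1 = 0.60. X is binomial(18, p).

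| True rate | P(X ≤ 7) | P(X = 8 or 9) | P(X ≥ 10) |
|---|---|---|---|
| 0.26 | 0.9301 | 0.0626 | 0.0073 |
| 0.60 | 0.0576 | 0.2055 | 0.7368 |

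Exact type I error is therefore 0.7% (stated 5%), correct rejection 93.0% (stated 80%) and type II error 5.8% (stated 5%). These rows are the baseline for step 4. That the cut-offs do not sit at the stated error rates is a separate matter.

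**3. Two response rates from the same data**

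The counts are assumed, because the plan gives none for this combination. Intervals are Clopper-Pearson 95%. Section 7.3 itself prescribes no interval; they are added for comparison.

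Case A: 5 CR or PR, 6 SD and 7 progressing, 18 treated.
- 7.1.1: 5/18 = 27.8% (9.7 to 53.5).
- 7.3, all 18 per protocol: (5 + 6)/18 = 11/18 = 61.1% (35.7 to 82.7).
- 7.3, 3 progressing patients excluded: 11/15 = 73.3% (44.9 to 92.2).

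Case B: 9 responders, no SD, 3 responders excluded from per protocol.
- 7.1.1: 9/18 = 50.0% (26.0 to 74.0).
- 7.3: 6/15 = 40.0% (16.3 to 67.7).

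In case A the 7.1.1 figure lies near the inactivity cut-off and the 7.3 figure near the activity cut-off. Case B shows that the 7.3 figure is not always the higher one.

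**4. Conditional illustration: the 7.3 numerator put into the 7.1.1 rule**

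The plan does not instruct this. Hold true CR plus PR at 0.26, add an assumed SD rate s, and take X as binomial(18, 0.26 + s).

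| s | 0.26 + s | P(declared effective) | P(declared ineffective) |
|---|---|---|---|
| 0 | 0.26 | 0.7% | 93.0% |
| 0.10 | 0.36 | 7.1% | 69.7% |
| 0.20 | 0.46 | 28.1% | 35.9% |
| 0.30 | 0.56 | 61.1% | 11.1% |

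P(X ≤ 7) falls to 0.80 at p = 0.3247, so s = 0.3247 − 0.26 = 0.065. P(X ≥ 10) reaches 0.05 at p = 0.3406, so s = 0.3406 − 0.26 = 0.081. About 6.5 points of SD breaks the stated 80% correct rejection, and about 8 points breaks the stated 5% type I error.

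For scale only: section 1.4.2 reports stable disease in 17 patients (63%) on nivolumab alone, a percentage that matches its 27 myeloma patients. That is not a rate for this combination, but it gives no support for assuming that SD will be rare.

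**The case against.** The best defence is that 7.1.1 governs. Its rule counts objective response, its analysis text specifies partial and complete, and it calls stable patients non-responders. With the synopsis, 5.2 and Appendix 13 pointing the same way, there is one sensible reading, and 7.3 never calls its rate the primary endpoint. On this view the defect is a stray term and an undefined label, and the inflated error rates describe a misuse that the plan does not direct.

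Much of this is right. The rule is not broken, and step 4 is conditional. A difference between the two rates is likely but not certain: they coincide if no patient has SD as best response, nobody is excluded as not per protocol, and no response first appears after cycle 4. The trailing restriction in 7.1.1 is probably leftover template text, and no passage identifies a treated patient whom it would remove. Time to Response and Duration of Overall Response are not listed endpoints, so their faults add little to the severity.

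What the defence does not supply is any text giving 7.1.1 precedence, or any definition of objective response beside the rule. Section 7.3 is an explicit definition. An analyst who follows it exactly will report a disease-control rate under the name of response rate. That is an error in the text, not an omission to be filled by common sense.

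**Conclusion.** The concern holds and must be fixed. The plan contains two incompatible definitions of its main efficacy measure, and the one in 7.3 cannot be compared with the 26% and 60% cut-offs. In the assumed example the gap is 61.1 − 27.8 = 33.3 percentage points from the same 18 patients. The size and direction of any real gap depend on the number of patients with SD as best response, on who is excluded as not per protocol, and on late responses; the plan gives none of these. The operating characteristics of the rule in 7.1.1 are unaffected as long as it is applied to partial and complete responses. They would be affected only if the 7.3 count were substituted.

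**What to change.** - In 7.3, delete SD from Response Rate, Time to Response and Duration of Overall Response.
- State once that the primary response rate and the 7/10-of-18 rule both count sCR, CR, VGPR or PR by Appendix 13, after 4 cycles, over all eligible patients who receive any treatment.
- Drop per protocol from Response Rate. The PFS definition in 7.3 uses the same undefined term, so define it there or remove it.
- In 7.1.1, remove the trailing restriction to a disease group and phase II assessment.
- Report disease control (including SD) and best response over all cycles as separate secondary summaries.
- Smaller wording points: the synopsis and 2.3 speak of 8 and 12 months under the primary endpoint, while 2.1 makes 8 and 12 cycles secondary, so align them. Say how the two consecutive assessments required by Appendix 13, footnote a, apply to a response first seen at the end of cycle 4. State how the fixed cut-offs apply if fewer than 18 patients are eligible and treated, since 6.8 does not replace withdrawals; with 15 patients and a true rate of 60%, the chance of 10 or more responses is 40.3%, against 73.7% with 18.

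The cost is a wording amendment, best made before outcome data are reviewed. Fixing the time point can move responses first reached after cycle 4 out of the primary count and into the secondary summary, and removing the restriction could change the 7.1.1 denominator. The reported rate will usually, though not always, be lower than under 7.3.
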